Aim 1. Maximize exercise-mediated recovery of limb muscles by using stimulation induced spinal plasticity. We will study the effect of limb training combined with Spike-Timing Dependent Plasticity (STDP) on motor function recovery. We will test the effect of three groups: (1) stimulation, (2) training +stimulation, and (3) training+sham stimulation. We hypothesize that the ability of training to promote recovery of limb motor function will be enhanced by eliciting STDP in upper and lower-limb. An important strength of this aim is the combination of training and STDP, which aims at enhancing the beneficial effects of motor training by promoting plasticity in the corticospinal pathway (Ellaway et al., 2007; Castel et al., 2009). Training effects on physiological pathways will be explored and correlated with hand/arm motor function and the site and extent of the lesion defined by structural MRI.

Aim 2. Maximize exercise-mediated recovery of limb muscles by using stimulation induced spinal plasticity. STDP has been shown to be effective in enhancing the recovery of residual limb function in humans with chronic incomplete SCI (Urbin et al., 2017). In this aim we will investigate the effect of the combination of extended STDP and training. We hypothesize the ability of training to promote recovery of motor function will be enhanced by eliciting STDP in the corticospinal pathway.

BACKGROUND:

After a SCI, many individuals present deficits in upper-limb and/or lower-limb function. Most SCIs are contusions and ~50% occur at the cervical level causing anatomically incomplete damage and bilaterally functional deficits to lower- and upper-limbs (Kakulas, 1999). Arm and leg function deficits limit daily-life activities, such as reaching and grasping, eating, writing, and walking which decreases the quality of life (Snoek et al., 2004). Regaining arm and leg function is considered the highest priority for improving the quality of life of individuals with SCI (Anderson, 2004).

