R) Participant reported spasticity: Individuals with SCI will grade the severity of spasticity with a four-point nominal scale (0=none; 1=mild; 2=moderate; 3=severe) to answer questions: 1) how would you rate the severity of your spasticity in your right biceps brachii, 2) triceps brachii, 3) quadriceps, and 4) tibialis anterior, 5) soleus?

S) Surveys: All SCI participants will be asked to complete the following SCI-CAT surveys during the pre-assessment and at the post-40 visits:

- (a) Ambulation: This questionnaire will ask the participant about their ability to do things like walk, run and jump.
- (b) Basic Mobility: This questionnaire will ask the participant about their ability to perform their daily routine.
- (c) Fine Motor: This questionnaire will ask the participant about their ability to pick up small objects.
- (d) Manual and Power Wheelchair Mobility: This questionnaire will ask the participant about their ability using a wheelchair.
- (e) Self-Care: This questionnaire will ask the participant about their ability to do activities of daily living such as getting dressed, bathing, and eating.

STUDY INTERVENTION(S) / INVESTIGATIONAL AGENT(S):

STDP protocol:

STDP and sham-STDP: During STDP, participants will have a maximum of 360 paired pulses of stimuli delivered every 1-10 s (~60 min) and a small cohort of participants (n=10) will have a maximum of 720 paired pulses of stimuli (up to 4 times per day) using the same delivery period. Corticospinal volleys will be evoked by TMS over the primary motor cortex and/or the spinal cord will be timed to arrive at corticospinal-motoneuronal synapses of each muscle ~1-2 ms before antidromic potentials evoked in motoneurons by peripheral nerve stimulation (PNS) and/or spinal root stimulation. During sham-STDP, a coil will be placed on the scalp of the participant to provide the participant with the feeling of having the coil on their head. This coil will not be connected to a TMS or any other device. A second coil will be placed ~10 cm behind the subject's head and triggered in the air every 1-10s for up to 720 stimuli to provide the subject with the same auditory sound produced by the TMS as the non-sham.

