All participants will exercise immediately after the stimulation paradigm. Upper-limb exercises will involve gross grasping, fine grasping, and hand cycle using an arm ergometer. During gross grasping, subjects will be asked to reach and grasp cylinders, blocks, cups and lids randomly presented on a table located in front of them at a height of ~20 cm. Then, subjects will be asked to reach and grasp the object to put it back on the table. These sets of movements will be repeated 20 times for each object with breaks as needed. During fine grasping, participants will perform similar movements but they will be asked to reach and grasp smaller objects (peg, bead, pinch pin, cube). During hand cycle, the arm ergometer will be used for 15 minutes and grasping gloves will be used as needed. Movements will be passive, active-assisted, or active depending on participant's ability to perform tasks. In addition, training will consist of grasping with the thumb and index finger targets of different diameters (1, 2.5, and 6 cm) in a vertical board (36x30") positioned in front of them. The board will contain 6 panels (12x15") which will light up individually by a computer cue. Each panel will have three LED lights to indicate grip strength to be exerted (red=30% MVC, blue=20% MVC, yellow=5% MVC). A reflective line in each target will identify the place to grasp, which will be modified to increase task difficulty. Force transducers will run along the sides of each target to communicate with LEDs. Kinematics and EMG signals will be acquired through surface electrodes. Subjects will be instructed to grasp the object between index finger and thumb as fast and accurately as possible holding the final posture for 3 s until the light disappear. 300 trials will be completed.

Lower Limb Training

All participants exercised immediately after STDP or sham-STDP. Lower-limb exercises will involve over-ground walking, treadmill walking, and stair climbing training. During locomotor training, subjects will use a body-weight support system with ~0-70% of body weight support. During treadmill training, subjects will walk at a speed of 0.1-0.3 m/s for 10 minutes using the body-weight support system.

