During stair climbing, subjects will climb up and down 4 steps with 3 full repetitions. Locomotor training+STDP protocol: In each session, STDP stimulation will be targeting the leg muscles at rest, and their effects will be tested on voluntary contractions. Locomotor training will be preceded by the STDP protocol. The locomotor training will consist of walking. The amount of weight support will be provided as needed by a body-weight support system and the level of support will be associated with gait kinematics which resemble unsupported walking. The body-weight support system is a robotic over ground arrangement for practicing a wide range of activities without the risk of falling. The support will be adjusted within and between sessions as necessary to prevent excessive knee flexion during stance phase or toe dragging during swing phase (Finch et al., 1991). Subjects will be encouraged to walk at their comfortable speed at which step kinematics are acceptable (no toe dragging, an adequate knee flexion during swing phase, adequate knee extension at initial stance phase, etc.). All subjects will be allowed to rest as needed during the training sessions. The starting and end points and guiding path will be marked with lines on the floor. Thirty five retro-reflective markers will be attached to the participant's body according to the Plug-In-Gait market set. While the participant is walking on the path, joint movements will be acquired by a 3dimensional motion capture system. The locomotor training session will consist of at least 3 sessions are expected to be completed per week as the participant is able. Missed sessions will be rescheduled according to the subject's availability.

STUDY TIMELINE:

Participants will be initially screened over the phone or in person to ensure eligibility based on established inclusion and exclusion criteria.

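### Both training sections tell all participants to exercise after stimulation, which contradicts the Aim 1 stimulation-only arm; nothing in the protocol says that arm omits exercise

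*Combined protocol and SAP*

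**What the plan says.** The Aim 1 arms are listed in three places, and the lists agree. The Objectives say: "We will test the effect of three groups: (1) stimulation, (2) training +stimulation, and (3) training+sham stimulation". The Aim 1 scheme in the Study Timeline shows the same three arms, and the GROUP factor in the Statistical Analysis section has the same three levels, with 15 participants per group and 45 in all.

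Two sections say who exercises. Upper limb training begins: "All participants will exercise immediately after the stimulation paradigm". Lower Limb Training begins: "All participants exercised immediately after STDP or sham-STDP". Neither makes an exception for any arm.

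Three other places bear on the point:

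- The STDP protocol section describes the stimulation as a procedure in its own right: "During STDP, participants will have a maximum of 360 paired pulses of stimuli delivered every 1-10 s (~60 min".
- The locomotor text describes a combined session: "Locomotor training will be preceded by the STDP protocol".
- The Study Timeline calls the Aim 1 visits training sessions, at least 10 of them. The compensation section refers to the same visits as combined stimulation and training.

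**The concern.** Training is the only thing that separates the stimulation-only arm from the training-plus-stimulation arm. A rule that everyone exercises after stimulation removes that separation. The arm name is then the only text telling staff to end a stimulation-only session after STDP, and the sections they would use to run a session say the opposite. At stake are the two Aim 1 comparisons that involve stimulation alone: what it does by itself, and what training adds to it.

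**Working it through.** The plan has no figure to reproduce on this point. The stated 45 participants cannot be rebuilt, because no effect size, standard deviation or within-person correlation is given, and the argument does not need it. The check sets the texts side by side and follows each reading through the planned comparisons.

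**Inputs.** Three Aim 1 arms (Objectives, Study Timeline, Statistical Analysis); 45 participants, 45 / 3 = 15 per arm (Statistical Analysis); Tukey comparisons after a repeated-measures ANOVA (Statistical Analysis); everyone exercises (both training sections).

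**What each arm receives**

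| Aim 1 arm | By the arm names | By the training sections as written |
|---|---|---|
| Stimulation | STDP | STDP, then exercise |
| Training + stimulation | STDP, then exercise | STDP, then exercise |
| Training + sham | Sham, then exercise | Sham, then exercise |

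In the last column the first two rows are identical. The delivered allocation is 15 + 15 = 30 training plus stimulation against 15 training plus sham, instead of 15/15/15.

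**Comparisons.** Write S, TS and TH for the expected outcomes in the stimulation, training-plus-stimulation and training-plus-sham arms. Three groups give 3 × 2 / 2 = 3 pairs. Under the training sections as written, S = TS, so:

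- S − TS = 0. The added effect of training cannot be seen.
- S − TH = TS − TH. This pair estimates the same quantity as the next one and says nothing about stimulation alone.
- TS − TH is unchanged. It is the comparison behind the Aim 1 hypothesis: "We hypothesize that the ability of training to promote recovery of limb motor function will be enhanced by eliciting STDP in upper and lower-limb".

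**Mixed practice.** Suppose a fraction p of the stimulation arm exercises. Assume that those who do have the same expected outcome as the training-plus-stimulation arm, and that who exercises is unrelated to prognosis. The first comparison then has an expected value of (1 − p) times the intended difference: all of it at p = 0, half at p = 0.5, none at p = 1. The documents give no basis for choosing p.

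**Aim 2.** It has a single arm, training plus stimulation, so the rule that everyone exercises fits it.

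**Number affected.** 15 of 45 is one third of Aim 1. The eligibility section gives 60 subjects for Aim 1, allowing for attrition. If those were allocated equally, 60 / 3 = 20 would be in the arm, again one third.

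**The case against.** The strongest reply is that the opening sentences cannot be meant for the whole trial. They stand under two headings, so read without limits they would put every participant through both limb programmes. The Study Endpoints section, however, refers to a separate group that does the lower-limb exercises. The sentences must therefore already be limited by their headings, and it is a short step to read them as covering only those assigned to train. The lower-limb mention of STDP or sham fits the two training arms alone and need not include the third. Three consistent arm lists also carry more weight than two opening sentences.

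Most of this stands. It makes a no-exercise stimulation arm the likely intent. It does not remove the conflict: limiting the sentences by limb programme is not the same as limiting them by arm, and no sentence does the latter. The visit labels do not help either way. They call all visits training sessions, but the same Study Timeline sentence describes Aim 1 visits as including stimulation, which is not true of the sham arm, so they are too loose to settle the question.

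A reader might also infer a dose error by multiplying the exercise amounts, such as "During hand cycle, the arm ergometer will be used for 15 minutes and grasping gloves will be used as needed" or "300 trials will be completed", by the minimum of 10 sessions. Such totals would require the amounts to be per session. They would describe what exercise is done and would not measure an error in the plan.

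**Conclusion.** The protocol is wrong as written, because it contradicts itself on what one randomised arm receives. The severity is minor.

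The harm depends on which text staff follow. If they follow the arm names, it is zero. If they follow the training sections, 15 of 45 Aim 1 participants receive another arm's intervention. Of the three pairwise comparisons, one has an expected difference of zero, one estimates the same quantity as another, and one is unaffected. This rests on the 15 per group in the Statistical Analysis section and assumes no effect size.

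A reader might go further and conclude that the Aim 1 hypothesis cannot be tested, or that the sponsor in fact intends everyone to train. The documents support neither. The hypothesis rests on training plus stimulation against training plus sham, which is the same under both readings, and the three arm lists point to an untrained stimulation arm.

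**What to change.** 1. In Upper limb training, replace the opening sentence with: *Participants assigned to a training arm (in Aim 1, training with stimulation or training with sham; or Aim 2) who are in the upper-limb programme start these exercises directly after their STDP or sham-STDP.* Use the matching sentence for the lower-limb programme in Lower Limb Training. Naming the programme matters: limiting the sentences by arm alone would send every trained participant to both programmes.
2. Add: *The Aim 1 stimulation arm receives STDP only, with no study exercise.*
3. In the Study Timeline, replace training session(s) with intervention session(s) at each of the six places where it occurs.

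If everyone is in fact meant to train, leave the training sections and instead correct the arm list in the Objectives and the Study Timeline, and the GROUP factor and per-group number in the Statistical Analysis section.

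The first route changes wording only. It needs no extra participants or procedures and leaves alpha and the analysis as they are.

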If eligible, participants will be asked to complete pre, post, and follow-up assessment sessions in addition to the training sessions. Each assessment will require 2-5 sessions. Participants will complete up to 135 training sessions with a maximum of 360 paired pulses of stimulation and a small cohort of participants (n=10) will complete up to 270 training sessions with a maximum of 720 paired pulse of stimulation (up to 4 times per day). This will be determined based on preliminary data. In Aim 1, participants will be tested before and after at least 10 training sessions with single site stimulation. In Aim 2, participants will be tested before and after at least 40 training sessions with multisite stimulation. If a training session is not completed or missed participants will be asked to recover that session in a timely manner.

AIM 1: Randomized controlled design

Pre-assessment: 1. Physiology 2. Kinematics 3. Function	Stimulation Training + stimulation Training + sham stimulation	Post-assessment: 1. Physiology 2. Kinematics 3. Function	Follow-up assessment: 1. Physiology 2. Kinematics 3. Function
--	--	---	--

AIM 2:

Pre-assessment: 1. Physiology 2. Kinematics 3. Function	Training + stimulation	Post-assessment: 1. Physiology 2. Kinematics 3. Function	Follow-up assessment: 1. Physiology 2. Kinematics 3. Function
--	------------------------	---	--

We anticipate that each participant will take about 2-10 months to complete the study procedures/testing. Follow-up assessments will be done 1-9 months after completion of protocol, one follow-up in the first 3 months and the last follow-up in the 4-9 months following the last completed session. We will evaluate the subject's ability to move their hands, arms, legs, feet and/or toes using the different physiological and functional tests as mentioned above. TMS measurements, CMEPS and EMG recordings may also be done at these follow-up assessments.

INCLUSION AND EXCLUSION CRITERIA:

We anticipate the screening of 500 subjects across the two aims (60 subjects for Aim 1, and 40 for Aim 2) who have incomplete SCI at the cervical/thoracic/lumbar level (C2-L2). This number accounts for an attrition rate of 50%. To account for screen failures we would like to ask for a total of 200 subjects.

- Inclusion criteria for SCI subjects:
 - (1) Male and females between ages 18-85 years
 - (2) SCI at least 4 weeks post injury
 - (3) Spinal Cord injury at or above L2
 - (4) ASIA A,B,C, or D, complete or incomplete

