Aim 1: Repeated-measures ANOVA and Tukey post hoc analysis will determine effects of GROUP (stimulation, training+stimulation, and training+sham), TIME (before, immediately after, and follow-ups around 3 and 6 months post intervention) on physiological and behavioral outcomes. For alpha (type I error) of 0.05 and 1-beta (power) of 0.8, 45 SCI participants (15/group) will be included.

Aim 2: Repeated-measures ANOVA and Tukey post hoc analysis will determine effects training stimulation, TIME (before, immediately after, and follow-ups around 9 months post intervention) on physiological and behavioral outcomes. For alpha (type I error) of 0.05 and 1-beta (power) of 0.8, 11 SCI participants will be included.

Audio/Video Taping:

We plan to audio and video taping some parts of the experimental session, upon subject consent (optional in the consent form). Recordings will be only of the experimental activities described in the protocol. The subjects' identity will be hidden if subjects do not explicit consent to be recognized from the video or audio. The audio and video records will be stored in a password-protected file on a USB drive in a locked cabinet in the PI's office at the Rehabilitation Institute of Chicago.

The audio and video records will be used only for:

- a) Medical or scientific publications;
- b) Presentation at conferences;

The audio and video records will be destroyed after the time period chosen in the consent form.

This study does not involve any other risk to the subject, beyond some sense of effort and mild fatigue. Fatigue will be assessed based on the subjects' verbal report. They will be explicitly invited to interrupt the experiment if they experience fatigue. All studies will be carried out in the hospital environment where medical care is immediately available if needed.

POTENTIAL BENEFITS TO PARTICIPANTS:

Participation in the experiment may result in no direct improvement or, in the rare and unanticipated event, worsening of the subject's condition, including prolonged recovery time.

DATA MANAGEMENT AND CONFIDENTIALITY:

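### The post-assessment is triggered by a minimum session count, so a participant who stops below it has no scheduled post-assessment and an ambiguous follow-up date

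*Combined protocol and SAP*

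**What the plan says.** Under Study Timeline in the combined protocol and SAP, the outcome visit follows a number of sessions, not a calendar date. For Aim 1: "In Aim 1, participants will be tested before and after at least 10 training sessions with single site stimulation". For Aim 2: "In Aim 2, participants will be tested before and after at least 40 training sessions with multisite stimulation". The upper limit is far above either minimum: "Participants will complete up to 135 training sessions with a maximum of 360 paired pulses of stimulation". Missed sessions are to be made up promptly, with no outer limit.

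Follow-up is dated in one sentence from two starting points. It begins "Follow-up assessments will be done 1-9 months after completion of protocol" and ends by placing "the last follow-up in the 4-9 months following the last completed session". The Statistical Analysis section uses a third phrase for Aim 1, "TIME (before, immediately after, and follow-ups around 3 and 6 months post intervention".

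Withdrawal of Participants lets people leave on request and lets the study end their participation. It mentions neither an end-of-treatment visit nor outcome collection after treatment stops. Statistical Analysis names repeated-measures ANOVA with Tukey comparisons, but gives no analysis set and no method for missing values. The Inclusion and Exclusion Criteria section expects 50% attrition.

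**The concern.** Consider someone randomised in Aim 1 who stops after session 7 because of fatigue, discomfort or travel, but would still attend an assessment. The trigger for the post-assessment is never reached, and nothing else in the plan calls this person in.

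Reaching 10 sessions happens after randomisation and can depend on the arm. The three arms are stimulation alone, training plus stimulation, and training plus sham. Active nerve stimulation can cause mild pain according to Risks to Participants, whereas the sham coil on the scalp is not connected to any device. If the people who reach the minimum differ between arms, randomisation no longer protects the GROUP or GROUP-by-TIME effect. Aim 2 has no comparison arm, so the issue there is narrower: the change would be estimated only in people who tolerated 40 sessions.

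**Working it through.** **1. The plan's own figure.** Aim 1 is set at 45 participants (15 per group) for alpha 0.05 and power 0.80. This cannot be reproduced, because no effect size, SD or within-person correlation is given. Solving backwards for a two-sided t-test of 15 v 15, with no multiplicity allowance, gives a detectable difference of d = 1.06. It serves below only as a yardstick.

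**2. The schedule applied to two Aim 1 participants.**

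| Visit | Reaches 10 sessions | Stops after session 7 |
|---|---|---|
| Post-assessment | Triggered | Not triggered; no other rule |
| Follow-up, dated from completing the protocol | Can be dated | No start date |
| Last follow-up, dated from the last session done | Can be dated | Can be dated |

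The two starting points can coincide for completers. They separate for early stoppers.

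**3. What reaches the analysis.** The Aim 1 TIME factor includes a value immediately after the intervention. Repeated-measures ANOVA in its usual form needs every time point. With no other missing-data method stated, the stopper in column three would probably drop out of the analysis even if the last follow-up were obtained.

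**4. How many people.** The documents list 60 for Aim 1 and expect 50% attrition, without saying when it occurs or which number it applies to.
- All loss before the post-assessment: 60 × (1 − 0.50) = 30, or 10 per group. Power at d = 1.06 is about 61%.
- No loss before it, or all 60 assessed regardless of sessions: 20 per group. Power is about 90% if partial treatment does not dilute the effect.
- 45 analysed: requires 1 − 45/60 = 25% loss.

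These bracket the loss of precision. They do not estimate it.

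**5. Bias, as illustration only.** If a fraction p of an arm stops below the minimum, and stoppers change g SD less than completers, the completer mean exceeds the whole-arm mean by p × g. The between-arm bias is (p₁ − p₂) × g.
- Equal stopping, same g: 0.
- Assumed 30% v 10%, g = 0.5: 0.20 × 0.5 = 0.10 SD.
- Assumed 30% v 10%, g = 1.0: 0.20 × 1.0 = 0.20 SD.

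The standard error of a 15 v 15 difference is √(2/15) = 0.37 SD, so 0.10 to 0.20 SD is about 0.27 to 0.55 of a standard error, and 9% to 19% of d = 1.06. Neither the stopping rates nor g comes from the documents.

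**6. Timing.** A rate of at least 3 sessions per week is stated only for locomotor training. At exactly 3 per week, 10 sessions take 10/3 = 3.3 weeks, 40 take 40/3 = 13.3 weeks, and 135 take 45 weeks. No rate is given for upper-limb training. The due date therefore cannot be derived for everyone, and a completer's post-assessment is not fixed in time either.

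**The case against.** The strongest reply is that the plan is silent and does not exclude anyone. Study Timeline first says, with no session condition, that eligible participants will be asked to complete pre, post and follow-up assessments. The minimum can be read as the intended amount of treatment, and no sentence says that people below it go unmeasured or unanalysed. That stands as a reading, but it does not supply a date for the visit, and the withdrawal and analysis sections do not supply one either.

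A reader might infer that an early stopper has no scheduled outcome at all. The documents do not support that: this person has a last completed session, so the last follow-up can be dated on that wording. A reader might also extend the harm to randomisation to both aims, but Aim 2 has a single arm.

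Differential stopping is not documented. For the contrast behind the main hypothesis, training plus stimulation against training plus sham, both arms train and sham delivery follows a similar timetable, so the time burden is close even if discomfort differs. The upper-limb section also says that all participants exercise, which blurs the stimulation-only arm. These points weaken any claim about the size of the bias. They do not remove the gap.

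**Conclusion.** The point holds in this form: a willing participant who stops below 10 (Aim 1) or 40 (Aim 2) sessions has no scheduled post-assessment, and the follow-up date is ambiguous. Followed as written, the plan makes Aim 1 a comparison of people who reached the minimum in their arm, and makes Aim 2 a before-after change in completers.

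The size cannot be computed from the documents. The 0.10 to 0.20 SD bias rests wholly on assumed stopping rates and an assumed completer-stopper gap, and could be zero. The power range of about 61% to 90% rests on 60 entering Aim 1, on when attrition falls, and on a true effect equal to the one that 45 would detect. With half the participants expected to be lost and a low-cost remedy available, the change should be made.

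**What to change.** - **Early stoppers.** State that every participant who stops below the minimum, unless consent to assessment is withdrawn, has the same post-assessment at the time it was due under the planned schedule. Measure that time from randomisation in Aim 1 and from the first session in Aim 2.
- **Target time.** The sponsor sets it separately for upper- and lower-limb training, since a session rate is given only for locomotor training. Completers use the same target window, so that timing does not depend on adherence.
- **Analysis.** Analyse Aim 1 participants in the arm to which they were randomised.
- **Follow-up.** Time both follow-ups, for everyone, from one anchor: a defined day of the scheduled post-assessment. A defined day is needed because each assessment takes 2 to 5 sessions.

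The cost is protocol wording and visits already planned. At $30 per assessment session, a stopper's post-assessment costs 2 × $30 = $60 to 5 × $30 = $150 in base participant payments. The downside is that the estimated effect may be slightly smaller, because partly treated participants are counted.
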